8.2.2. Extent of Exposure (Maternal)

Summaries will be presented only for mothers by initial treatment, retreatment and total.

Duration of exposure (hour) is defined as the total number of hours a subject is exposed to any study drug and will be presented as the total number of hours from the first dose date/time (Day 1) to the last dose date/time (date/time of last dose - the date/time of first dose).

The duration of exposure to study drug by treatment will be summarized using descriptive statistics for Maternal Safety Population. The duration of exposure will then be classified into one of the following categories: 0 to \leq 1 hour, >1 and \leq 6 hours, >6 and \leq 12 hours, >12 and \leq 24 hours, >24 and \leq 36 hours, >36 and \leq 48 hours and >48 hours and will be presented as the number and percentage of subjects in each duration category.

The total volume administered during the infusion and the number of infusion interruptions will be summarized using descriptive statistics.

In addition, reasons for IP deviation, escalation and interruption will also be listed. Details of IP deviation will be finalized before DBL.

Also, inadequate therapeutic response will be summarized and listed.

A summary of each subject exposure will be presented in a listing.

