2013]. At the clinical study site, the volume required to make up the dose is withdrawn from 1 or several drug product vials and aseptically transferred into a 0.9% NaCl infusion bag to get the required concentration. The final mixture is a clear, colorless to slightly colored solution. The infusion solution is chemically stable for up to 24 hours under ambient conditions.

Because the IV dosing instructions for retosiban and atosiban differ, a double-dummy technique will be used to ensure blinding. For subjects randomized to retosiban, an unblinded pharmacist or other qualified individual will prepare the retosiban IV solution and a placebo infusion matched for the atosiban loading (bolus) dose and continuous infusion. Likewise, subjects randomized to atosiban will receive the atosiban loading (bolus) dose and continuous infusion and a placebo infusion matched for retosiban IV administration (see [Table 3](#); detailed instructions are provided in the Study Pharmacy Manual).

Atosiban solution for injection will be supplied by the unblinded pharmacist or other qualified individual as a prefilled syringe, whereas a prefilled syringe with 0.9% NaCl solution will be used for the matched placebo. Normal saline (0.9% NaCl) solution will be used for preparing the retosiban or atosiban admixtures for continuous infusion (see [Table 4](#)). Normal saline (0.9% NaCl) solution will also be used as the placebo solution matched to the infusion rates for retosiban or atosiban (see [Table 4](#); detailed instructions are provided in the Study Pharmacy Manual). The normal saline solutions will be provided by the investigative center.

Details of the dose preparation are described in the Pharmacy Reference Manual. The infusion bags and syringes containing the solution for administration will be clearly labeled by site staff with the protocol number, subject number, infusion rate, and dosing session number.

Investigational product must be stored in a secure area under the appropriate physical conditions for the product. Access to and administration of the IP will be limited to the investigator and authorized site staff. Investigational product must be dispensed or administered only to subjects enrolled in the study and in accordance with the protocol.

[Table 3](#) and [Table 4](#) summarize the retosiban and atosiban IP, respectively, and other study treatment.

Table 3 Retosiban Investigational Product and Other Study Treatment

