5.2. Managing Dose Interruptions

Temporary interruptions of the IP are permitted. The following procedures should be followed in the event of a retosiban dose interruption:

- If the interruption is <60 minutes, restart the IP infusion.
- If the interruption is from 60 to 90 minutes, inclusive, administer a loading dose at a rate equal to one-half of the prior loading dose rate. For example, if the loading dose rate prior to the interruption was 240 mL/hour over 5 minutes, administer the loading dose at 120 mL/hour over 5 minutes, and then resume the infusion.

- If the interruption is >90 minutes, administer a loading dose at a rate equal to the prior loading dose rate. For example, if the prior loading dose was administered at 240 mL/hour over 5 minutes, administer the loading dose at 240 mL/hour over 5 minutes, and then resume the infusion.

For atosiban dose interruptions, resume the infusion at the same rate that was used before the dose interruption.

Any changes in the dose rate, corresponding start and stop times, and the reason for an interruption must be recorded in the eCRF.

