11.3. Appendix 3: Treatment States and Phases

Study treatment start date/time and/or stop date/time are determined by the infusion of IP administered. For retreated subjects, start date/time and stop date/time for both initial treatment and retreatment will be derived.

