11.5.2. Study Population

Demographics

Age for Mother

- GSK standard IDSL algorithms will be used for calculating age where birth date will be imputed as follows:
 - [1] Date of birth of any subject will have this imputed as '30th June'.
 - [2] If a subject is recorded as an adolescence in CRF and imputed date of birth in [1] is > 18 years old, the last possible date to be 18 years old will be assigned. For example, an adolescence's randomization date is 30Jun2016 and birth year is 1998. Imputed date of birth in [1] is 30Jun1998 and age is 19 years old. Then 29Jun1998 will be used as birth date to keep the subject in adolescence category.
- Birth date will be presented in listings as 'YYYY'.

Body Mass Index (BMI)

- Calculated as Weight (kg) / [Height (m)]²

Extent of Exposure

- Number of hours of exposure to study drug will be calculated using dates from the trial medication form. The duration of exposure in days will be based on the formula:

Duration of Exposure in Hours = (Treatment Stop Date/Time (in minutes) – Start Date/Time (in minutes))/60

- If there are any treatment interruptions during the study, then the exposure data will be adjusted accordingly.

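### SAP 8.2.2: first-to-last-dose duration counts the untreated gap in the total for retreated women, and total volume does not show how much active drug was given

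*SAP*

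**What the plan says.** **Duration.** SAP 8.2.2 opens with a definition by concept: "Duration of exposure (hour) is defined as the total number of hours a subject is exposed to any study drug". The same sentence then makes it operational: "total number of hours from the first dose date/time (Day 1) to the last dose date/time (date/time of last dose - the date/time of first dose". That section also sets the levels of reporting: "Summaries will be presented only for mothers by initial treatment, retreatment and total". Duration is given as descriptive statistics and in seven categories, the last being more than 48 h.

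Two appendices bear on this. SAP 11.3 states: "For retreated subjects, start date/time and stop date/time for both initial treatment and retreatment will be derived". SAP 11.5.2 uses stop minus start and adds: "If there are any treatment interruptions during the study, then the exposure data will be adjusted accordingly". It gives no method for the adjustment and does not mention the interval between courses. It also introduces a formula in hours as a duration in days.

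**Amount.** SAP 8.2.2 states: "The total volume administered during the infusion and the number of infusion interruptions will be summarized using descriptive statistics". This follows Protocol 8.3.5.2.1, which also specifies volume. Neither document plans a summary in milligrams, although the protocol's dose limits are in milligrams: 300 and 582 mg for retosiban (Table 3) and 330 mg for atosiban (Table 4).

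**Design.** The trial is double-dummy. Protocol 5.1 says: "Likewise, subjects randomized to atosiban will receive the atosiban loading (bolus) dose and continuous infusion and a placebo infusion matched for retosiban IV administration". Protocol Table 3 applies the inadequate-response increase to the saline line as well. Protocol Table 4 gives atosiban a fixed schedule.

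**The concern.** An exposure table should tell the reader how long women were on drug and how much they received. Here the duration formula can include days without any infusion, and the SAP does not say whether the total is the sum of the two courses or the span from first to last dose. Two programmers could produce different versions of Table 3.01.

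Volume has a different problem. Each woman receives one active line and one saline line, and the rate increase is always made on the retosiban or retosiban-placebo line. A larger volume therefore means more drug in one arm and only more saline in the other. What is at stake is the clarity of the exposure description that accompanies the safety profile.

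**Working it through.** **Protocol dose figures, from rate times time**
- Retosiban, no increase: 6 + 6 × 48 = 294 mg (stated limit 300 mg).
- Retosiban, increase at 1 h: 6 + 6 × 1 + 6 + 12 × 47 = 582 mg (stated 582 mg).
- Atosiban: 6.75 + 18 × 3 + 6 × 45 = 330.75 mg (stated limit 330 mg).

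The rates therefore reproduce the stated figures exactly or to within 2%.

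**Duration in retreated women.** Protocol 3.1.3.1 allows retreatment 24 h or more after the inpatient treatment phase is completed. The literal rule gives course 1 + gap + course 2; the infused time is course 1 + course 2.

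| Courses | Gap | Literal total | Infused |
|---|---|---|---|
| 48 h + 48 h | 24 h (minimum) | 120 h | 96 h |
| 48 h + 48 h | 7 days (assumed) | 264 h | 96 h |
| 48 h + 48 h | 14 days (assumed) | 432 h | 96 h |
| 10 h + 10 h | 24 h (assumed) | 44 h | 20 h |

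Two full courses fall in the category above 48 h either way, so only the descriptive statistics move. The two 10 h courses move from the >12 to 24 h category to the >36 to 48 h category. That last row counts the 24 h from the end of the infusion. If it ran from the end of a nominal 48 h phase, the gap would be 38 + 24 = 62 h and the literal total 10 + 62 + 10 = 82 h.

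Effect on an arm mean of the total, assuming 48 women per arm (97 were randomised): one retreated woman with two full courses adds 24/48 = 0.5 h at the minimum gap and 336/48 = 7 h at an assumed 14-day gap. The documents give no count of retreated women.

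**Volume in the atosiban arm.** Inputs are the rates in Protocol Tables 3 and 4. Assumptions: a full 48 h, each 5-minute load inside the 48 h, no interruption and no CYP3A4 adjustment.
- Atosiban line: 0.9 + 24 × 3 + 8 × 45 = 432.9 mL.
- Saline line, no increase: 20 + 20 × 47.917 = 978.3 mL. Two-line total: 1,411.2 mL.
- Saline line, increase at 1 h: 20 + 20 × 0.917 + 20 + 40 × 46.917 = 1,935.0 mL. Two-line total: 2,367.9 mL.

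| Increase at | Two-line total | Change | Saline line alone |
|---|---|---|---|
| 1 h | 2,367.9 mL | +68% | +98% |
| 6 h | 2,267.9 mL | +61% | +88% |
| 12 h | 2,147.9 mL | +52% | +75% |
| 24 h | 1,907.9 mL | +35% | +51% |
| 47 h | 1,447.9 mL | +3% | +4% |

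The atosiban dose is 330.75 mg in every row. In the retosiban arm, on the same clock, an increase at 1 h also raises the two-line volume by 68%, while drug rises from 0.3 × 978.3 = 293.5 mg to 0.3 × 1,935.0 = 580.5 mg (+98%). These differ slightly from 294 and 582 mg because the loads are counted inside the 48 h.

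**The case against.** The plan has a fair defence.

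- **Duration.** Each course is summarised on its own and has its own derived start and stop times, so the gap cannot enter those rows. For the total, the conceptual definition and SAP 11.5.2 both point to infused time, and a sensible programmer would probably use it. This limits the problem to one row. It does not remove it, because the only explicit formula in SAP 8.2.2 gives the other answer and SAP 11.5.2 does not mention the gap.
- **Volume.** It is the protocol's own measure, so the SAP has not departed from anything. That stands; milligrams would supplement it.
- **Dose increases.** A reader might infer that they are hidden. They are not: SAP 6.2 counts them by treatment group, SAP 8.2.2 lists the reasons, and Table 3.02 and Listing 30 cover inadequate response.
- **Dose limits.** A reader might infer that a breach of a limit could not be found. Milligrams can be derived, since concentrations are fixed and Protocol 5.2 says: "Any changes in the dose rate, corresponding start and stop times, and the reason for an interruption must be recorded in the eCRF". The plan simply does not summarise them.
- **Safety results.** It is tempting to treat exposure as the denominator of the safety profile. The documents do not support this. SAP 8.2.3 reports numbers and percentages of subjects, no exposure-adjusted rate is planned, and SAP 11.3.1 and 11.3.3 assign events to phases from course-specific times.

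**Conclusion.** The point holds as a minor finding with two parts.

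1. The literal duration formula overstates the total for any retreated woman by the whole gap between courses: at least 24 h, or 25% for two full courses. It contradicts its own definition and is not reconciled with SAP 11.5.2. The effect on arm means depends on how many women were retreated and on the length of their gaps, neither of which is given.
2. Volume alone cannot separate a real increase from one made on the placebo line, and the SAP does not say which lines count. The 68% is a maximum, not a typical value. It requires both lines to be summed, an increase at 1 h and a full 48 h of infusion. Nor does it follow that observed volumes will be equal in the two arms; that would require the same timing of increases and the same completion.

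No efficacy or adverse event result depends on either part.

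**What to change.** In SAP 8.2.2, replace the first-to-last formula with the sum over courses of (stop minus start minus interruptions), applied to initial treatment, retreatment and total. Use the same wording in SAP 11.5.2, state there how interruptions are subtracted, and correct its reference to days.

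Keep volume, as the protocol specifies, but split it by active and placebo line. Add milligrams of active drug by arm and by whether the rate was increased: active-line volume × 0.3 mg/mL for retosiban, and the 6.75 mg bolus plus active-line infusion volume × 0.75 mg/mL for atosiban (check: 6.75 + 432 × 0.75 = 330.75 mg). Add a footnote that increases in the atosiban arm were made on the placebo line.

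The cost is SAP wording and minor programming of Table 3.01 and Listing 21. The rates and times are already required in the eCRF, so no new data are needed. The change should be made before database freeze.

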8.2.3. Adverse Events

AEs will be coded using the Medical Dictionary for Regulatory Activities (MedDRA) coding dictionary. A mapping of the MedDRA primary system organ class (SOC) and preferred term (PT) that each verbatim term has been coded to will be provided in a listing. In general, AEs will be presented in descending order from the SOC with the highest total incidence (that is, summed across all treatment groups) for any adverse event within the class to the SOC with the lowest total incidence. Within the SOC level, AEs will be presented in descending order from the PT with the highest total incidence to the PT with the lowest total incidence. If the total incidence for any two or more PTs within an SOC is equal, the PTs will be presented in alphabetical order. A PT will not be

presented if no adverse events occur within the level. At each level of summarization, a subject is counted only once if the subject reported one or more events.

The number and percentage of subjects with any AE started on or after the first study treatment will be summarized by treatment group in the tables. All AEs will be listed.

8.2.3.1. All Adverse Events

The number and percentage of subjects reporting at least one AE for each SOC and PT will be reported by treatment group. The summary will include both non-serious and serious AEs. A listing of all adverse events will be provided. Also, the above summary will be produced by subgroups defined in Section **Error! Reference source not found.**

The AE will be summarized by maternal, fetal and neonatal events, separately. Also, the maternal AE by treatment phase (on-treatment, post-treatment) defined in Section 11.3.3 will be summarized.

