obstetrician. For those subjects who deliver at the investigative center, a placental tissue sample will be obtained at the time of delivery for central histopathology examination and a cord blood sample will be collected for potential genetic research and biomarker assays. If delivery occurs within 12 hours of investigational product (IP) (retosiban or atosiban) completion or discontinuation, the cord blood sample will also be used for the pharmacokinetic (PK) assessment, and, if required, a corresponding maternal blood sample will be collected for PK analysis (see Section 6.5.1). Likewise, a breast milk/colostrum sample will be collected for PK analysis in women who deliver at the investigative center and produce breast milk within 12 hours after IP completion or discontinuation. A maternal post-delivery assessment will be conducted by telephone within 6 weeks of delivery.

During the Maternal Post-Delivery Assessment Phase, the subject will be contacted by telephone within 6 weeks of delivery for a post-delivery assessment, including an assessment of AEs (\pm 2 weeks), status of breastfeeding (\pm 2 weeks), and completion of the EPDS (-2 weeks/+6 weeks) and the EQ-5D-5L (-2 weeks/+6 weeks).

During the Neonatal Medical Review Phase, the neonatologist subinvestigator will conduct a comprehensive review of the newborn's medical records, including any admission to an intensive or specialized care unit and any hospital readmission or outpatient surgery, from delivery through 28 days EDD, where EDD is defined as 40^{0/7} weeks' gestation for all subjects.

The subject or other legal guardian for the infant will also be asked to consent to participate in a separate long-term study to follow infants for safety and neurodevelopment outcomes. The consenting process for the infant follow-up study can occur at any time during the study that is appropriate and convenient for the subject or legal guardian, such as during the Inpatient Randomized Treatment Phase or at the face-to-face post-infusion assessment visit.

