6.3. Safety

The timing for all safety assessments is outlined in the Time and Events Schedule [Table 5](#).

Maternal:

- Incidence of reported AEs and SAEs
- Significant changes in vital signs and clinical laboratory tests
- Incidence of treatment-limiting toxicities including both clinical and laboratory etiology causing subject to discontinue study treatment

- Maternal AEs of special interest
 - Maternal death
 - Chorioamnionitis and its complications
 - Clinical chorioamnionitis, PPROM, endomyometritis, wound infection, pelvic abscess, bacteremia, septic shock, disseminated intravascular coagulation, and adult RDS
 - Placental abruption
 - Postpartum hemorrhage - postpartum hemorrhage and/or retained placenta (as assessed by AEs, time to expulsion of the placenta, assessment of uterotonic agents used, and change in hemoglobin from baseline value to 24 to 48 hours post-delivery adjusting for mode of delivery)
 - Pulmonary edema
- Incidence of women scoring 12 or higher on the EPDS

Fetal:

- Incidence of reported AEs, including SAEs
- Fetal acidosis
- Fetal AEs of special interest
 - Intrauterine fetal demise
 - Category II or III fetal heart rate tracing (defined according to ACOG Practice Bulletin 106 [[ACOG](#), 2009])
 - Fetal inflammatory response syndrome characterized by cord blood interleukin-6 >11 pg/mL, funisitis, or chorionic vasculitis

Neonatal:

Note: Information collected from the time of birth through 28 days post EDD.

- Neonatal Apgar scores (at 1 and 5 minutes after birth), growth parameters (weight, length, and head circumference) at birth and at discharge, and documentation of any complications
- Incidence of reported AEs and SAEs
- Neonatal AEs of special interest are of interest because of their relationship to maternal chorioamnionitis and will include the following:
 - Neonatal death
 - Asphyxia
 - Infections (early onset neonatal sepsis, septic shock, pneumonia, meningitis)
 - RDS
 - Hypotension

- IVH/periventricular leukomalacia with cysts or porencephaly
- Bronchopulmonary dysplasia
- Neonatal acidosis
- Hyperbilirubinemia
- Necrotizing enterocolitis (any modified Bell's staging criteria)
- Hypoxic ischemic encephalopathy

Maternal and neonatal disease-related events (DREs) to be reported are described in Section 6.3.7.

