6.3.8. Time Period and Frequency of Detecting AEs and SAEs

The investigator or site staff is responsible for detecting, documenting, and reporting events that meet the definition of an AE or SAE.

Adverse events and SAEs will be collected from the start of study treatment and until the follow-up contact (see Section [6.3.10](#)) at the time points specified in [Table 5](#).

Medical occurrences that begin prior to the start of study treatment but after obtaining informed consent may be recorded on the Medical History/Current Medical Conditions section of the eCRF. Additionally, if a condition with a start date predating Day 0 (Screening) is subsequently discovered, the condition should be recorded in the Medical History eCRF.

Any SAEs assessed **as related** to study participation (e.g., protocol-mandated procedures, invasive tests, or change in existing therapy) or related to a GSK product will be recorded from the time a subject consents to participate in the study up to and including any follow-up contact.

All SAEs will be recorded and reported to GSK/PPD within 24 hours, as indicated in Section [6.3.11](#).

Investigators are not obligated to actively seek AEs or SAEs in former study subjects. However, if the investigator learns of any SAE, including a death, at any time after a subject has been discharged from the study, and he/she considers the event reasonably related to the study treatment or study participation, the investigator must promptly notify GSK/PPD.

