Adverse Events (Fetus)	
 • Any partial dates for adverse events will be flagged to data management. If the full date cannot be ascertained, the following assumptions will be made: 	
 
 Start Date	 
 • If the partial date is a start date, a '01' will be used for the day and 'Jan' will be used for the month. • However, if these results in a date are prior to the first study treatment date, then the first study treatment date will be assumed to be the start date. • The AE will then be considered to start on-treatment (worst case). 	
 
 End Date	 
 • If the partial date is a stop date, a '28/29/30/31' will be used for the day (dependent on the month and year) and 'Dec' 	
 
	Start Date	
 • If the partial date is a start date, a '01' will be used for the day and 'Jan' will be used for the month. • However, if these results in a date are prior to the first study treatment date, then the first study treatment date will be assumed to be the start date. • The AE will then be considered to start on-treatment (worst case). 	End Date	
 • If the partial date is a stop date, a '28/29/30/31' will be used for the day (dependent on the month and year) and 'Dec'
Start Date	
 • If the partial date is a start date, a '01' will be used for the day and 'Jan' will be used for the month. • However, if these results in a date are prior to the first study treatment date, then the first study treatment date will be assumed to be the start date. • The AE will then be considered to start on-treatment (worst case). 					
End Date	
 • If the partial date is a stop date, a '28/29/30/31' will be used for the day (dependent on the month and year) and 'Dec' 					

Element	Reporting Detail
	
will be used for the month.
 
• However, if these results in a date are after the birth date or fetal death date, then the birth date or fetal death date will be assumed to be the end date.

11.7. Appendix 7: Primary and Sensitivity Analyses for Primary and Key Secondary Endpoints with Missing Data

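### Separate fetal and neonatal SAE and AESI percentages rest on observation windows that shift with time to delivery; a pregnancy-level table over one fixed window would supplement them cheaply

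*SAP*

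**What the plan says.** **Start of counting.** Protocol 6.3.8 states "Adverse events and SAEs will be collected from the start of study treatment and until the follow-up contact". SAP 8.2.3 tabulates "The number and percentage of subjects with any AE started on or after the first study treatment".

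**End of the fetal window.** The SAP gives no explicit stop. Its partial-date rule for fetal events (SAP 11.6.2.2) caps a late imputed stop date: "then the birth date or fetal death date will be assumed to be the end date".

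**Neonatal window.** The neonatal part of Protocol 6.3 carries the line "Note: Information collected from the time of birth through 28 days post EDD". Protocol 3.1 fixes the reference point: "where EDD is defined as 40^{0/7} weeks' gestation for all subjects". Neonatal collection therefore closes at 44 0/7 weeks, whenever birth occurs.

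**Tabulation.** SAP 8.2.3.1: "The number and percentage of subjects reporting at least one AE for each SOC and PT will be reported by treatment group", and "The AE will be summarized by maternal, fetal and neonatal events, separately". SAEs (SAP 8.2.3.4) and AESIs (SAP 8.2.3.6) are reported in the same way. The split by treatment phase is specified for mothers: "Also, the maternal AE by treatment phase (on-treatment, post-treatment) defined in Section 11.3.3 will be summarized". No rate per unit of time, fixed landmark or pooled fetal-neonatal table is planned for SAEs or AESIs.

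**The concern.** The boundary between the fetal and neonatal tables is delivery, and time to delivery is the primary endpoint. If retosiban prolongs pregnancy, its fetuses are observed for longer and its newborns for less time than those on atosiban. A percentage with at least one event tends to rise with the length of observation. Part of any difference in either table could then reflect where the boundary fell and not a difference in risk.

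This matters because Protocol 2.2 sets out to describe fetal and neonatal safety relative to atosiban, and side-by-side percentages are what readers will compare. Later birth may also truly reduce complications of prematurity. The neonatal table alone cannot separate that benefit from shorter observation.

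**Working it through.** The plan states no window lengths and no adverse event rates, so there is no planned figure to reproduce here. The 9.5-day effect is taken as given from Protocol 8.2.1.

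**1. Windows.** Let T be time to delivery and G gestational age (GA) at randomization, both in days. The close is 44 x 7 = 308 days.
- Fetal window = T
- Neonatal window = 308 - G - T
- Sum = 308 - G, which does not involve treatment

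Neonatal window by GA at birth, (44 - GA) x 7: 30 weeks, 98 days; 38 weeks, 42 days; 41 6/7 weeks, 15 days.

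**2. Shift at the design effect, by hand.** Protocol 8.2.1 gives the strata mix (7/13/27/53%) and 55% of atosiban women delivering within 3 weeks. Assumed: stratum mid-points, early deliveries at a mean of 10.5 days, the rest at 38.5 weeks.
- Mean GA = 0.07 x 25 + 0.13 x 27 + 0.27 x 29.5 + 0.53 x 32.5 = 30.45 weeks
- Total window = (44 - 30.45) x 7 = 94.85 days
- Atosiban fetal window = 0.55 x 10.5 + 0.45 x (38.5 - 30.45) x 7 = 31.1 days
- Atosiban neonatal window = 94.85 - 31.1 = 63.7 days
- Shift: 9.5/31.1 = +31% fetal; 9.5/63.7 = -15% neonatal

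Other delivery assumptions gave 28% to 34% and 14% to 16%.

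**3. Same check by simulation.** 300,000 per arm; early deliveries uniform over 0 to 21 days; later births with mean 39 weeks and SD 1.3 weeks (assumed). The early share on retosiban was set to give a shift of 9.6 days. Mean fetal window: 32.7 to 42.3 days (+29%). Mean neonatal window: 62.1 to 52.5 days (-15%).

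**4. From windows to percentages.** The same hazard was applied in both arms, so any difference is artefact. Two timing patterns were tried. Constant: the hazard is flat over the window. Front-loaded: it decays with a mean of 2 days from dosing (fetal) or 7 days from birth (neonatal). Control rates are assumed.

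| Control rate | Fetal on retosiban, constant | Neonatal on retosiban, constant | Fetal, front-loaded | Neonatal, front-loaded |
|---|---|---|---|---|
| 10% | 12.8% | 8.5% | 10.2% | 10.0% |
| 30% | 37.7% | 26.0% | 30.5% | 29.9% |
| 50% | 60.6% | 44.4% | 50.8% | 49.9% |
| 70% | 79.5% | 64.1% | 71.0% | 69.9% |

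The artefact is 2.8 to 10.6 points (fetal) and 1.5 to 5.9 points (neonatal) under constant hazards. It is at most 1.0 and 0.1 points if events are front-loaded.

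**5. Noise.** Standard error of a difference at 30%: sqrt(2 x 0.3 x 0.7/48.5) = 9.3 points with the 97 enrolled (SAP 1) split evenly; 5.0 points with the planned 165 per arm.

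**6. Pooled window.** Counting from first dose to 28 days post EDD, with a hazard of 0.01 per day in both arms, gave 60.6% in each.

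**The case against.** **Window length is not bias.** The tables report percentages, and converting one into the other needs event timing. A reader might infer that retosiban must look worse for the fetus and better for the newborn, so that the benefit-risk reading is confounded by efficacy. The documents do not support that: they give no event rates or timing, and several features point to clustering. The composite's definition of respiratory distress syndrome is tied to the first 24 hours of life (Protocol 6.2.4). Neonatal AESIs include asphyxia, acidosis and early-onset sepsis. Fetal heart rate is scheduled during infusion, at one visit and just before delivery, with weekly telephone contact in between. This objection stands, and it sets the lower end of the range.

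**The plan already bridges delivery in part.** A reader might also infer that nothing is combined across birth. The neonatal composite counts fetal or neonatal death and major morbidity through 28 days post EDD (Protocol 6.2.4, SAP 11.5.4). The most-common-event table is limited to on-treatment events (SAP 8.2.3.3), fetal heart rate category is split by phase (SAP 8.2.6.2), and safety subgroups use GA at randomization (SAP 5.1.2). All of this is true, but none of it gives SAEs or AESIs a common window.

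**The fixed close is defensible.** It follows every infant to the same postmenstrual age, which suits diagnoses such as bronchopulmonary dysplasia, assessed at 36 weeks or later. This stands: the close itself need not change.

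**Safety is descriptive, in a trial stopped at 97.** No formal test is planned (Protocol 8.3.5.2, SAP 5.2), and sampling noise may exceed the artefact. This lowers the priority without removing the point.

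**Conclusion.** The structural point holds. The fetal and neonatal windows move one-for-one in opposite directions with the primary endpoint, and the separate tables use plain percentages. The window shifts (about +30% and -15%) rest on the 9.5-day design effect and on assumed delivery timing; no observed effect is claimed.

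The consequence for the reported percentages is uncertain. It runs from negligible to several points according to event timing, which the documents do not give. At the enrolled sample size even the upper end (about 11 points) is of the same order as one standard error. This is therefore a low-cost improvement to the safety display. It is not evidence that the planned safety comparison is wrong in a known direction.

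**What to change.** Add to SAP 8.2.3, by treatment group, with the pregnancy as the unit and the Maternal Safety Population as the denominator:

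- one table for SAEs and one for AESIs, counting any fetal or neonatal event from first dose through 28 days post EDD;
- the AESI table shown with and without Category II/III fetal heart rate tracings, so that common tracings do not dominate the count.

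The planned window is then set only by GA at randomization, which is a stratification factor, and nothing is conditioned on GA at birth, a post-randomization outcome. Keep the separate fetal and neonatal tables, with a footnote that their observation windows depend on time to delivery.

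Two alternatives are not recommended. Events per infant-week would mislead if events are front-loaded: similar counts over less time would inflate the retosiban rate by about 18% (62.1/52.5 = 1.18). A common interval after birth could be no longer than 15 days if it is to include a birth at 41 6/7 weeks. An infant born at 28 weeks reaches 36 weeks only after 56 days, so bronchopulmonary dysplasia would be missed.

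Cost: a few extra descriptive tables from data already collected, and a pooled count that mixes different event types. SAP 1 leaves decisions on the final analyses open until database freeze, so the change fits the plan's timetable if made before then.
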